#### **7.6.5. Clinical Laboratory Evaluation**

Samples for clinical chemistry, hematology, and other lab parameters will be collected during screening, before study drug administration, on day 1 (and day 15 in milademetan arm) of each treatment cycle and at the treatment discontinuation visit.

Laboratory data will be summarized in tables using descriptive statistics for baseline and each cycle/visit. Descriptive statistics will be calculated on both the actual score and the change from baseline score. Additionally, clinically significant abnormalities in laboratory results will be summarized for the post-baseline cycles/visits using frequencies and percentages. Shifts from baseline to minimum post-baseline and baseline to maximum post-baseline value (according to NCI Common Toxicity Criteria version 5.0 grading) will be presented for each treatment group.

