## 6.2 Milademetan Administration

[figure not shown]
Milademetan 260 mg QD will administered orally on Days 1 to 3 and Days 15 to 17 of each 28-day cycle. Milademetan will be administered at the clinical site on the indicated visit days (Cycle 1: Days 1, 3, and 15, Cycles 2 and 3: Days 1 and 15, and Cycles 4+: Day 1 only; [Table 1](#))

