### 6.2.1 Milademetan Dose Modifications

## **6.3 Trabectedin Administration**

Trabectedin will be administered at 1.5 mg/m^2 BSA as a 24-hour IV infusion, every 3 weeks through a central venous line. Clinical laboratory assessments must be resulted and evaluated prior to administration of study drug on the day of administration.

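### Worst-value laboratory shift tables compare arms sampled every 2 and every 3 weeks with no visible common period, so at equal per-draw risk milademetan shows more shifts

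*SAP*

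**What the plan says.** SAP 7.6.5 takes laboratory samples at screening and then "on day 1 (and day 15 in milademetan arm) of each treatment cycle and at the treatment discontinuation visit". Protocol 6.2 gives milademetan "orally on Days 1 to 3 and Days 15 to 17 of each 28-day cycle". Protocol 6.3 gives trabectedin "as a 24-hour IV infusion, every 3 weeks through a central venous line".

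On analysis, SAP 7.6.5 states: "Laboratory data will be summarized in tables using descriptive statistics for baseline and each cycle/visit". It also counts clinically significant abnormalities over post-baseline cycles or visits, and presents for each treatment group, by CTCAE grade, "Shifts from baseline to minimum post-baseline and baseline to maximum post-baseline value". The visible text gives no common period, no matching of draws, no time at risk, and no statement on whether unscheduled values enter the minimum and maximum. SAP 7.6.6 uses the same sampling days and the same cycle indexing for vital signs.

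Three other places matter. Protocol 6.2 lists on-site milademetan days that include Day 15 in Cycles 1 to 3 but only Day 1 from Cycle 4. The protocol synopsis assumes a median PFS of 6 months on milademetan and at most 3 months on trabectedin. Protocol 8.9 refers the timing of laboratory samples to Tables 2 and 5, which are not readable in the text supplied.

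**The concern.** A patient's minimum or maximum over follow-up can only become more extreme as values are added. If one arm is sampled more often, or for longer, its worst-value shift table shows more shifts even when the drugs carry the same risk at each draw. Here the arm sampled more often, and expected to stay on treatment longer, is the investigational one.

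Protocol 3.2 makes the safety profile of milademetan versus trabectedin a secondary objective, so these tables will be read across arms. Protocol 8.9 also has clinically significant laboratory results reported as adverse events, so unequal sampling could reach those tables too. The documents do not allow that effect to be sized.

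Indexing by cycle raises a separate problem. With 28-day and 3-week cycles, the same cycle number falls at different times since first dose.

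**Working it through.** The documents give no laboratory abnormality rate and no draw count, so there is no plan figure to reproduce. The check counts scheduled draws and converts them to the share of patients with at least one shift.

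**1. Draws through Week 12 (day 85), with Cycle 1 Day 1 predose as baseline.**
- Milademetan, Days 1 and 15 of 28-day cycles: days 15, 29, 43, 57, 71, 85, so k = 6. Protocol 6.2 gives the same count, since Day 15 is an on-site day in Cycles 1 to 3.
- Trabectedin, Day 1 every 3 weeks: days 22, 43, 64, 85, so k = 4.

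**2. Share with any shift = 1 − (1 − p)^k.** The per-draw risk p is an assumption, equal in both arms, and draws are taken as independent.
- p = 2%: 1 − 0.98^6 = 11.4%; 1 − 0.98^4 = 7.8%.
- p = 5%: 1 − 0.95^6 = 26.5%; 1 − 0.95^4 = 18.5%.

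**3. Correlated draws.** A random-intercept logistic model with marginal p = 5% gives, at Week 12:

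| Random-intercept SD | Milademetan | Trabectedin |
|---|---|---|
| 1 | 23.7% | 17.2% |
| 2 | 18.3% | 14.2% |
| 3 | 14.5% | 11.8% |

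The gap shrinks from 8.0 points under independence to 2.7 points but keeps its direction.

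**4. Planned medians.** Median PFS (6 and 3 months) stands in for time on treatment, which is an assumption. Trabectedin has 4 draws. Milademetan has 13 if Day 15 draws continue in every cycle, or 9 if they stop after Cycle 3. At p = 5%:
- 13 draws: 1 − 0.95^13 = 48.7%, against 18.5%.
- 9 draws: 1 − 0.95^9 = 37.0%, against 18.5%.

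These counts leave out the discontinuation draw, which adds one in each arm.

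**5. How much of step 4 is exposure?** The split depends on the order in which it is made.
- At 3 months in both arms, milademetan has 6 draws (26.5%). Frequency then explains 26.5 − 18.5 = 8.0 points. Longer exposure explains 48.7 − 26.5 = 22.2 points, or 37.0 − 26.5 = 10.5 points with 9 draws.
- At 6 months in both arms, trabectedin has 8 draws (33.7%). Exposure then explains 33.7 − 18.5 = 15.2 points. Frequency explains 48.7 − 33.7 = 15.0 points, or 37.0 − 33.7 = 3.3 points with 9 draws.

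Exposure is therefore between half (15.2/30.2) and about four-fifths (15.2/18.5) of the gap.

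**6. Equal exposure over longer periods (draws, milademetan against trabectedin).**

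| Week | Day 15 in every cycle | Day 15 in Cycles 1 to 3 only |
|---|---|---|
| 12 | 6 vs 4 | 6 vs 4 |
| 24 | 12 vs 8 | 9 vs 8 |
| 36 | 18 vs 12 | 12 vs 12 |
| 48 | 24 vs 16 | 15 vs 16 |

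**7. By-cycle alignment.** Cycle 5 Day 1 is 4 × 28 = 112 days after first dose on milademetan (Week 16) and 4 × 21 = 84 days on trabectedin (Week 12). If abnormalities are counted per visit, p = 5% gives 5% in both arms. If they are counted once per cycle, milademetan with two draws gives 1 − 0.95² = 9.75% against 5%. The SAP does not say which count applies.

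**The case against.** The strongest reply is that the draw counts are not settled. Protocol 6.2 lists Day 15 as an on-site day only through Cycle 3, while SAP 7.6.5 samples on Day 15 of every cycle. Under the Protocol 6.2 pattern, the excess at equal exposure has gone by Week 36 and is slightly reversed by Week 48. Tables 2 and 5 could also add draws in either arm. This stands as a limit on the longer-term figures. It does not touch the 6 against 4 by Week 12, which fits both sections, subject to those tables.

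A common-period or visit-window rule may exist in text that is not available: the body of Protocol Section 9 and part of SAP 7.6 are missing from the copy reviewed. This also stands, so the point concerns the visible plan only.

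The tables are descriptive, no test between arms is planned in SAP 7.6.5, and SAP 7.6.2 already reports treatment duration and number of cycles. The synopsis and SAP 2.2 word the safety objective without a comparator. All true, and the reason this is a modest improvement. But nothing visible links the exposure summary to the shift tables, and Protocol 3.2 does name the comparison.

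A reader might infer that the by-cycle summaries also make milademetan look more toxic. The documents do not support that: means and per-visit percentages do not rise with the number of draws, and misaligned time can push either way. A reader might also extend the point to ECGs. SAP 7.6.7 schedules standard on-treatment ECGs only in Cycle 1, so there are no later cycles to misalign.

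**Conclusion.** The point holds for the worst-value shift tables. On the visible schedule, milademetan has 6 scheduled post-baseline draws and trabectedin 4 by Week 12. At equal per-draw risk that inflates the milademetan column by 3.6 points at p = 2% and 8.0 points at p = 5% with independent draws. At 5%, within-patient correlation reduces the excess to between 6.5 and 2.7 points.

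Over the full treatment period the gap is larger, but a reader should not attribute 48.7% against 18.5% to visit frequency. Half or more of it is longer exposure, PFS is only a proxy for time on drug, and the figure falls to 37.0% if Day 15 draws stop after Cycle 3.

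Nor do the documents show that the finished tables will be tilted against milademetan overall. Equal per-draw risk is an assumption made to isolate the artefact, and the true rates are unknown. The by-cycle summaries have a time-alignment defect without a fixed direction. The consequence is confined to interpretation of descriptive safety tables; the primary PFS analysis is not affected.

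**What to change.** Keep the planned tables and make these changes:

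- Add worst-value shift tables limited to a common period, for example through Week 12 from first dose, using one scheduled value per common week window in each arm, chosen by a prespecified rule. For instance, four 3-week windows (days 2–22, 23–43, 44–64, 65–85), taking the scheduled value nearest the window's end, give at most 4 values per patient in both arms. At p = 5% that is 18.5% in each arm for patients followed to Week 12.
- Beside the full-period shift tables, report the number of draws and the time at risk by arm, and state whether unscheduled values enter the minimum and maximum.
- Index by-visit laboratory and vital-sign summaries by week from first dose.
- Reconcile the Day 15 sampling in SAP 7.6.5 with the visit days in Protocol 6.2, and check Tables 2 and 5 for other draws.

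No new data are needed. The cost is a few more tables and a windowing rule. The common-period tables use fewer values and can miss an extreme result that the full-period tables would show, which is why both are needed. They also do not remove differences from patients who stop before Week 12, so time at risk should be reported for them as well.

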#### **7.6.6. Vital Signs and Physical Examinations**

Vital signs, including systolic and diastolic blood pressure, pulse, and body temperature, as well as weight will be collected during screening and on day 1 (and day 15 in milademetan arm) of each cycle.

Summary tables will include descriptive statistics (number of patients, mean, std, median, Q1, Q3, min, and max) for baseline and each cycle/visit. Descriptive statistics will be calculated on both the actual score and the change from baseline score.

Physical examinations will be collected during screening, before study drug administration, on day 1 (and day 15 in milademetan arm) of each treatment cycle and at the Treatment Discontinuation Visit. Physical examination results will be summarized, and the frequency of clinically significant changes will be tabulated by treatment.

#### **7.6.7. Electrocardiograms**

Single standard 12 lead digital ECG will be performed during screening, at Cycle 1 Day 1 (and Day 15 in milademetan arm), and on the treatment discontinuation visit. For the triplicates at baseline, the average will be included in the summary.

The ECG (measured after resting in a supine position for 10 minutes) will include heart rate, rhythm, and RR, PR, QRS, QT and QTc intervals. The ECG will be read and interpreted at the investigational site for patient safety monitoring, and documentation stored with the source documents.

[REDACTED]

All ECG parameters, their change from baseline, and the frequency of abnormal ECG events will be summarized across study time points by treatment arm using descriptive statistic. All ECG values will be listed by patient.

[figure not shown]
#### **7.6.9. Liver Function Test Results**

A listing will be generated for patients potentially meeting Hy's Law criteria (total bilirubin  $\geq 2 \times$  upper limit of normal [ULN] and aspartate aminotransferase [AST] or alanine aminotransferase [ALT]  $> 3 \times$ ULN at any time during the study). Plots or tables of on therapy peak total bilirubin vs. peak AST (or ALT) will also be generated to help identify potential Hy's Law cases.

#### **7.6.10. ECOG Performance Status**

ECOG performance status will be assessed at screening, Day 1 of every cycle (and Day 15 in milademetan arm), and at treatment discontinuation.

The ECOG status will be included in the baseline and demographic variables. The number and percentages of patients in each ECOG category will be presented by treatment.

## **8. CHANGES TO THE ANALYSES PLANNED IN THE PROTOCOL**

This section is to be filled out if there are any changes to the analyses prior to finalization of the SAP.

## **LIST OF PLANNED TABLES, FIGURES, AND LISTINGS**

### **List of Planned Tables**

Category	Title
Disposition	Summary of Randomization
	Summary of Analysis Population
	Summary of Subject Disposition
	Summary of Protocol Deviations
	Summary of Follow-up Time
Demography and Baseline Characteristics	Summary of Demographics
	Summary of Baseline Characteristics
Medical History	Summary of Medical History
Cancer History	Summary of Prior Cancer History
	Summary of Prior Anticancer Medications
	Summary of Prior Anticancer Radiotherapy
	Summary of Prior Anticancer Surgical Therapy
	Summary of Biomarkers
Concomitant Medications	Summary of Concomitant Medications
	Summary of Concomitant Surgery
Study Medication	Summary of Treatment Exposure
	Summary of Treatment Dose Reduction
	Summary of Treatment Dose Hold
Efficacy	Summary of Progression-Free Survival by Central Review
	Summary of Progression-Free Survival by Investigator
	Summary of PFS in Subgroups
	Summary of Objective Response Rate
	Summary of Duration of Response
	Summary of Disease Control Rate
	Summary of Overall Survival
	Summary of Overall Survival in Subgroups
	Concordance of Central PFS and Local PFS

Category	Title
	Summary of Subsequent Anti-cancer Treatment
Health Outcomes	Summary of EORTC QLQ-C30 Observed Results and Change from Baseline
	Summary of EORTC QLQ-C30 Mixed Model Between Treatment Comparison
	Summary of Time to EORTC QLQ-C30 Deterioration
Safety	Summary of Overall Safety
	Incidence of TEAE by Preferred Term
	Incidence of TEAE by System Organ Class, Preferred Term, and Grade
	Incidence of Serious Adverse Events by Preferred Term
	Incidence of Serious Adverse Events by System Organ Class, Preferred Term, and Grade
	Incidence of TEAE Related to Study Treatment
	Incidence of TEAE Leading to Study Discontinuation
	Incidence of TEAE Leading to Study Drug Reduction
	Incidence of TEAE Leading to Study Drug Hold
	Incidence of Grade 3 or 4 TEAE by System Organ Class, and Preferred Term
	Summary of TEAE with Incidence $\geq 10\%$ by Preferred Term
	Summary of Death
	Summary of TEAE of Special Interest
Laboratory	Mean and Mean Change from Baseline in Numeric Laboratory Data: Hematology/ Clinical Chemistry
	Shift from Baseline in Laboratory Data: Hematology/ Clinical Chemistry
Vital Signs	Mean and Mean Change from Baseline in of Vital Signs Data
	Frequency Table of Potentially Clinically Significant Vital Signs Data
Physical Exam	Summary of Physical Examination
ECG	Mean and Mean Change from Baseline in ECG Data
	Summary of Abnormality in ECG
Liver Function	Summary of Liver Function Parameters for Potential Hy's Law
ECOG	Summary of ECOG by Visit

## List of Planned Figures

Category	Title
Efficacy	Kaplan-Meier Plot of Progression-free Survival by Central Review
	Kaplan-Meier Plot of Progression-free Survival by Investigator
	Forest Plot of Progression-free Survival by Central Review
	Forest Plot of Progression-free Survival by Investigator
	Kaplan-Meier Plot of Overall Survival
	Forest Plot of Overall Survival
	Kaplan-Meier Plot of Duration of Response by Central Review
	Kaplan-Meier Plot of Duration of Response by Investigator
QoL	Mean Plot of Observed EORTC QLQ-C30 by Visit
	Mean Plot of EORTC QLQ-C30 Change from Baseline by Visit
Safety	Hy's Law Plot

## List of Planned Data Listings

Category	Title
Disposition	Listing of Protocol Deviations
	Listing of Enrollment by Country
Safety	Listing of Serious Adverse Events
	Listing of Adverse Events Leading to Treatment Discontinuation
	Listing of Adverse Events Leading to Hospitalization
	Listing of Adverse Events Leading to Dose Reduction
	Listing of Adverse Events Leading to Dose Hold
	Listing of Treatment Related Adverse Events
	Listing of Deaths
	Listing of Potential Hy's Law Cases
Study Drug	Listing Study Drug Lot Numbers

